3.2 Study Outcome Measures

3.2.1 Primary

The primary outcome is toothbrushing performance through the Month 6 visit, measured with a Bluetooth-enabled toothbrush, and expressed as a mean of the number of qualifying half-day toothbrushing episodes per week. A toothbrushing session recorded with the app qualifies to contribute to the weekly count if it lasts at least one minute and occurs within one of the 14 possible half-day windows during a week; only one session per half-day window contributes to the weekly count, which can range from 0 to 14.

A participant qualifies for weekly drawing eligibility as follows:

- Low threshold - if the child's teeth were brushed at least once per day for at least one minute each day of the week;
- High threshold - if the child's teeth were brushed at least once per half-day for at least one minute each day of the week.

3.2.2 Secondary

Intermediate toothbrushing performance measures are as follows:

- Mean of the number of qualifying half-day toothbrushing episodes per week, through 1 month for short-term effects
- Mean of the number of qualifying half-day toothbrushing episodes per week, through the Month 3 visit for mid-term effects after any novelty effect would be expected to end,
- Mean of the number of qualifying half-day toothbrushing episodes per week, from Month 6 visit to Month 12 visit for longer-term effects

For the outcomes listed above, the minimum qualifying length of time is 1 minute.

Additional secondary oral health measures will be ascertained:

- Debris Index of the Simplified Oral Hygiene Index for Maxillary Incisors (OHI-MIS) to measure plaque on primary maxillary incisor facial (labial) tooth surfaces at Month 6 and Month 12 visits (mean of 4 ordinal scores)
- TP pump weight change (grams) at Month 6 and Month 12 visits
- Binary measure of Association of State and Territorial Dental Directors Basic Screening Survey (ASTDD BSS) untreated caries status ($dt>0$) at Month 6 and Month 12 visits
- Binary measure of ASTDD BSS caries experience status ($dmft>0$) at Month 6 and Month 12 visits; m is missing due to caries only
- Binary measure of ASTDD BSS severe caries ($dmft 4+$) status at Month 6 and Month 12 visits; m is missing due to caries only
- Binary measure of a dental visit in the past 12 months, obtained through EHS ChildPlus database which records annual dental visit and other required health screenings

To assess potential mediation effects of beliefs (behavioral, normative, and control) on intermediate outcomes (intentions, salience, and habit) and primary outcome (toothbrushing performance), the aforementioned primary and secondary outcome measures will be assessed. Behavioral, normative, and control beliefs will be collected via the BRFQ at each study visit (see Section 8.3). Intentions, salience, and habit will be collected with components of the BRFQ (e.g. intentions to brush child's teeth in the next 6 months, preventive habits for one's self and for one's child, age started brushing study child's teeth.).

To estimate the short- and long-term cost effectiveness and return on investment of rewards in improving parent/caregiver behaviors and children's oral health, net costs will be ascertained (as detailed in Section 12.4).

During the qualitative process evaluations at the Month 6 and Month 12 visits, the following will be ascertained: oral health behaviors and health habits, dental care

motivation behavior, toothbrushing and reactions to the powered toothbrush, toothpaste pump use, toothbrush syncing, Sonicare app use, text message reminders, opportunity costs, incentives, overall satisfaction, and perspectives on behavior data tracking for personal use and outside monitoring purposes.

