2 INTRODUCTION: BACKGROUND INFORMATION AND SCIENTIFIC RATIONALE

2.1 Background Information

Early childhood caries (ECC) remains the most prevalent chronic childhood disease in the United States (Vargas et al., 1998; Poland & Hale, 2003; CDC, 2001) and poses a serious threat to child welfare, particularly among economically disadvantaged, underserved, and migrant children (Ramos-Gomez et al., 2007; DHF, 2006). National ECC prevalence (any decayed, extracted, or filled primary teeth (deft)) among 2–5 year olds was 23% in 2011–2012 (Dye et al., 2015). Mexican-Americans had double the ECC severity of non-Hispanic Whites (Wiener et al., 2015).

Since dental disease risk increases as a child's teeth erupt (ADA, 2014), brushing with fluoridated toothpaste (TP) (smear for children under 3 years old, pea-sized for those 3–6 years old) for 2 minutes twice daily (Creeth et al., 2009) can help prevent ECC. For 1- to 2-year old children, professional application of fluoride varnish (FV) over 2 years is efficacious (Weintraub et al., 2006; Gansky et al., 2007) and the standard of care for prevention. Powered toothbrushes can provide better plaque removal than manual toothbrushes (Yacoob et al. 2014), but may also have a short-term novelty effect. Research participants using powered toothbrushes may also experience a Hawthorne effect from knowing they are in a research study. Both the novelty and Hawthorne effects have been reported to abate after 12 weeks among college students in a randomized controlled trial (RCT) evaluating plaque levels (McCracken et al. 2000).

Types of Rewards. Incentives are a common component of health promotion programs. Recognizing the important role that incentives can play, NIH has placed the evaluation of incentives on health-related behaviors among its highest priority areas for health economics research (NIH, NOT-OD-16-025, 2015).

Lottery prizes (a type of monetary incentive) have been more successful than non-monetary incentives for encouraging more physical activity (Wing et al., 1996), smoking

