4 STUDY DESIGN

We will conduct a stratified RCT testing the impact of monetary rewards on ECC preventive behaviors and oral health. Eligible child-parent/caregiver participant dyads will be consented, enrolled, and, following a 2 week run-in, randomized within strata and permuted blocks in equal allocation to one of two groups: 1) Monetary Rewards or 2) Delayed Reward Control. Strata will be based on site and smartphone operating system. The intervention will be offered for 6 months, and children (ages 6 months through <48 months) will be followed for 12 months to determine reward effects on dental visit attendance, toothbrushing, fluoride TP use, OHI-MIS plaque score , and caries screening status. Results will inform researchers and public health practitioners on the longer-term maintenance of behavioral changes and oral health screening status following removal of the rewards.

The study population will be predominantly low income Hispanics/Latinos who are parents/caregivers with children enrolled in, or waitlisted for, one of the participating Los Angeles County EHS or affiliated day care center programs. After enrollment parents/caregivers will use powered toothbrushes for a 2 week run-in to ensure their technology works and they are willing to follow study procedures; after the enrollment visit and run-in, randomization will occur at a separate visit. Participants who are unable to provide data during the run-in period will not be randomized or continue in the study.

Participants in the Monetary Reward group will be eligible to earn one of two incentive amounts every week for the first 6 months of the trial. A participant who meets a low or high threshold will earn entry in that week's drawing for financial incentives (See Section 6.1 for additional details).

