5 STUDY ENROLLMENT AND WITHDRAWAL

5.1 Subject Inclusion Criteria

Child

To be eligible to participate in this study, a child must meet all of the following criteria, to be verified during a screening visit:

- at least 6 months old but less than 4 years (48 months).
- at least 2 fully erupted teeth.
- enrolled in, or waitlisted for, one of the participating Los Angeles County EHS or affiliated day care center or area clinic programs.

Parent/caregiver

To be eligible to participate in this study, a parent/caregiver must meet all of the following criteria, to be verified during a screening visit:

- Provide signed and dated informed consent form in English or Spanish.
- Agree to comply with all study procedures and be available for the duration of the study.
- Aged 18 and older.
- Speak either English or Spanish and self-reported ability to read and write either English or Spanish.
- Be a parent or caregiver of a child at least 6 months old but less than 4 years (48 months), with at least 2 fully erupted teeth and enrolled in, or waitlisted for, one of the participating Los Angeles County EHS or affiliated day care center or area clinic programs.
- Not be planning to move residence for the next 18 months outside the greater Los Angeles area.
- Own a smartphone with the Google Play or iTunes store and be willing to download and install the smart powered TB app at the Screening visit and keep it installed for the duration of the project. [If the app cannot be properly installed by the baseline visit, the participant will not be randomized.]
- Be willing to be contacted via text-messaging (SMS) for study related notifications, such as incentives earned or reminders to sync the TB.

Stakeholder

To be eligible to participate in the stakeholder interviews, a staff member must meet all of the following criteria:

- Be a staff member at a participating study site (e.g. EHS or affiliated day care center).
- Verbally agree to participate after being provided a study information sheet.

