8.7.3 Fluoride Toothpaste Pump

Study participants will be instructed to use fluoridated TP based on the recent ADA consensus guideline (2014) that recommends all children use fluoride TP to help prevent dental disease. The study will use Colgate Maximum Cavity Protection Pump Fluoride Toothpaste (Colgate-Palmolive Company) (mild bubble fruit flavored).

The parents/caregivers will be instructed on how to dispense a smear or pea-sized amount (depending on child's age) of fluoride TP onto the toothbrush for the child, as per study guidelines.

If a child experiences an adverse reaction to the fluoride TP, he/she will be provided clinical guidance (e.g., discontinue use of the product); based on clinical judgment and appropriate input from oversight groups, use may be re-started. However, no modification of study product dosage will be made.

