12.4 Final Analysis Plan

Intent-to-treat (ITT) analyses standard in incentive based behavioral economics studies will be utilized (e.g. Halpern *et al.* 2015, Patel *et al.* 2016). Generalized linear mixed models (GLMMs) will be used to compare primary and secondary outcomes over time between groups. GLMMs make fewer missing data assumptions than other methods, which assume missing data are missing completely at random. Identity link will be used for numeric (interval) outcomes (e.g., mean number of qualifying half-day toothbrushing episodes per week, through Month 6 visit; mean OHI-MIS plaque score; and TP pump weight change). The group x time interaction will also be assessed; short-term effects will be assessed for 1 month of the intervention, mid-term effects after the novelty effect of powered toothbrushing usually ends for the Month 3 Visit, and long-term effects for the Month 6 Visit (primary outcome), as well as, maintenance of behavior after removing the incentives for the Month 12 Visit. Recent, powerful Precision Medicine methods which do not inflate Type I error will be used to detect heterogeneity of treatment effects by groups of participants based on baseline characteristics (e.g., Lazar *et al.* 2013). Multiple imputation using chained equations (MICE) for arbitrary missingness patterns (Raghunathan *et al.* 2001; van Buuren 2007) will be used for sensitivity analyses. Supplemental analyses will also explore: a) trajectories of mean number of qualifying half-day brushing episodes per week over time; as well as b1) variability in morning brushing times, b2) variability in evening brushing times, and c) variability in weekday versus weekend brushing times associated with mean number of qualifying half-day brushing episodes, OHI-MIS plaque scores, and ASTDD BSS caries screening measures.

To examine potential impact of timing of drawing reward communication time, GLMM analyses as above will be performed comparing the weekly and quarterly drawing result communication arms for primary and secondary outcome data from Month 12 to Month 18.

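### Toothpaste use is compared in raw grams with no stated age term, although the instructed amount per brushing depends on the child's age: a small, avoidable loss of precision in one secondary outcome

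*Combined protocol and SAP*

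**What the plan says.** Section 3.2.2 lists "TP pump weight change (grams) at Month 6 and Month 12 visits" among the additional secondary oral health measures. In section 12.4, "Identity link will be used for numeric (interval) outcomes", and toothpaste pump weight change is one of the examples given. No covariate, scaling or stratification is named for it.

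Section 2.1 gives the amount per brushing as "smear for children under 3 years old, pea-sized for those 3–6 years old". Section 8.7.3 says that caregivers will be shown how to "dispense a smear or pea-sized amount (depending on child's age) of fluoride TP onto the toothbrush for the child".

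Children enter at 6 to under 48 months (section 5.1) and are followed for 12 months (section 4). The pump is weighed at Month 6, replaced, and the new one weighed at Month 12 (section 7.2). Randomization is stratified on site and phone type (section 5.4.1). Child age appears in section 12.4 only as a possible source of heterogeneity in the treatment effect.

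**The concern.** Grams used are the number of brushings times the amount per brushing. If families follow the instruction, two children brushed equally often can return pumps of different weight because one is past the third birthday. Under the entry criteria some children are below the switch throughout, some are above it throughout, and those entering at 24 to under 36 months reach it during follow-up.

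The resulting variance has nothing to do with the reward, and it can be predicted from information held at randomization. Left in the error term, it lowers the precision of the toothpaste comparison. A chance difference in age between arms would also move that comparison. Testing whether the effect differs by age, as section 12.4 plans, does not remove age from the error term of the main comparison.

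**Working it through.** **The plan's own figures.** The documents give no power, SD or sample size for toothpaste weight. The primary-outcome figure reproduces: 91 per group, difference 2.65, SD 6.0, two-sided alpha 0.05 gives 84.2% by the noncentral t (stated: 84%). The pilot brushing CVs in section 12.2 also reproduce closely: 4.8/5.5 = 0.87, and 32/63 = 0.51 (stated: 0.514, from unrounded inputs). I use 0.51 and 0.87 for variation in brushing.

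**Assumptions not in the documents.**
- Entry age is uniform on 6 to 48 months.
- A pea-sized amount weighs r times a smear, with r from 1.5 to 3.
- Families dispense as instructed and switch at 36 months.
- The number of brushings is independent of age.
- Pump intervals are taken as months 0–6 and 6–12. The first pump is in fact handed out at screening, about two weeks earlier.

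**Step 1: time past the switch.** Let p be the fraction of the interval at or above 36 months. For pump 1, p = 0 for entry age up to 30 months, rises linearly to 1 at 36 months, and is 1 above that.
- Mean p = (12 + 3)/42 = 0.357.
- Mean p² = (12 + 2)/42 = 0.333.
- Var p = 0.333 − 0.357² = 0.206, so SD = 0.454.
- About 6/42 = 14% of children cross the switch within this interval.

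**Step 2: variance share.** The amount per brushing is proportional to 1 + (r − 1)p, with squared CV

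A = (r − 1)² × 0.206 / [1 + (r − 1) × 0.357]².

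With brushing CV b, the squared CV of raw grams is (1 + A)(1 + b²) − 1, and age accounts for A divided by that. Example, r = 2.5, b = 0.51: A = 0.196; 1.196 × 1.260 − 1 = 0.507; share = 0.196/0.507 = 39%. If other variation in dispensing or sharing with CV 0.5 is added, the denominator becomes 1.196 × 1.260 × 1.25 − 1 = 0.884 and the share 22%.

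| r | A | Share, b = 0.51 | Share, b = 0.87 | With extra CV 0.5, b = 0.51 | With extra CV 0.5, b = 0.87 |
|---|---|---|---|---|---|
| 1.5 | 0.037 | 12% | 4.5% | 6% | 3% |
| 2 | 0.112 | 28% | 12% | 15% | 8% |
| 2.5 | 0.196 | 39% | 18% | 22% | 12% |
| 3 | 0.280 | 46% | 22% | 28% | 15% |

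For pump 2, mean p = (18 + 3)/42 = 0.50 and Var p = 20/42 − 0.25 = 0.226. The same formula gives 4% (r = 1.5, b = 0.87) to 41% (r = 3, b = 0.51) without the extra variation. If enrolment in practice stopped at 36 months, the pump-1 share at r = 2.5 would be 25% (b = 0.51) or 10% (b = 0.87).

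**Step 3: what an age term buys.** Removing a share s of the variance is worth a factor 1/(1 − s) in sample size. At r = 2.5 this is 1/(1 − 0.387) = 1.63 for b = 0.51 and 1/(1 − 0.178) = 1.22 for b = 0.87. At the bottom of the range it is 1/(1 − 0.045) = 1.05.

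**Step 4: chance imbalance.** With 91 per arm, one standard error of the between-arm difference in mean p is 0.454 × √(2/91) = 0.067. With equal brushing, that shifts mean grams by (r − 1) × 0.067 / [1 + (r − 1) × 0.357]. This is about 3% at r = 1.5 and 8% at r = 3, against the 25% ratio used for planning in section 12.2.

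**The case against.** The strongest reply is that nothing here is an error. Allocation is 1:1 and random, so age adds the same expected variance to both arms. The unadjusted comparison is valid, and chance imbalance is already reflected in its standard error. A reader might infer that raw grams bias the comparison; the documents do not support that. This part of the reply stands in full.

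It also stands that the stakes are low. This is one of six additional secondary measures, with no power claimed. A reader might treat it as the trial's adherence check on the brush log, but no section gives it that role: it is called an oral health measure, and section 4 speaks of fluoride toothpaste use. For that target raw grams are a natural quantity, and dividing grams by the instructed amount would answer a different question.

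The variance shares rest on assumptions. The documents give no weight for a smear or a pea, no age distribution and no SD for pump weight. Section 8.3 asks whether others in the household used the pump, and visits may vary by 28 business days either way; both add variation that shrinks age's share. The age-3 cut is stated in section 2.1, while section 8.7.3 says only that the amount depends on age. Teaching the amount is listed at screening but at no later visit, so a switch exactly at the third birthday is not documented. It would be wrong to state as fact that equal brushing gives very different grams.

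Finally, section 12.4 lists no covariates for any outcome. A reader might infer that age adjustment is ruled out; it is only unstated.

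None of this removes the core point: the plan's own instructions make grams depend on age, and the analysis text does not use age to absorb it.

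**Conclusion.** The point holds as a low-severity matter of precision. The outcome is in raw grams, the instructed amount depends on age, the switch lies inside the entry range, age is not a stratum, and no age term is stated. Age therefore adds variance that a covariate known at randomization could remove in part.

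The working range for that variance, about 4% to 46% of first-pump grams or 3% to 28% with further dispensing variation, runs from negligible to substantial. No single value in it should be quoted as the trial's figure. It depends on the assumed ratio, uniform entry age, dispensing as instructed and the chosen variation in brushing.

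**What to change.** Add one sentence to section 12.4: the toothpaste-weight models will adjust for the fraction of each scheduled pump interval (0–6 and 6–12 months) that the child spends at or above 36 months, computed from age at randomization.

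Use the scheduled intervals, not the actual visit dates. Visit dates arise after randomization, and a covariate built on them would no longer be fixed at baseline. Do not add an analysis of grams scaled by the instructed amount, because the documents give no smear or pea weights to scale by.

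The cost is SAP wording and one derived variable from child age, which is already verified at screening. No data collection is added.

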7.1.1 Screening Visit (Visit 1, T = business day -10)

- Explain purpose and procedures of study to prospective parent/caregiver participant. Verify inclusion/exclusion criteria.
- Obtain and document consent from subject on study consent form electronically with DocuSign.
- Study staff download app on parent's/caregiver's smartphone and sync the TB to his/her smartphone. Walk parent through the app. Explain how to sync.
- Administer CAPI questionnaire to parent/caregiver.
- Record medical history and perform ASTDD BSS dental screening on child participant's teeth (by blinded dental provider); record decay and assess treatment urgency. Children with urgent treatment needs will be referred with a warm handoff to staff at the corresponding dental clinic.
- Apply plaque disclosing agent to child's teeth (by blinded dental provider).
- Take extraoral photograph(s) of the facial surfaces of child's anterior teeth.
- Give the family the Oral Hygiene Kit, which includes the smart powered toothbrush and fluoride TP pump. Attach label with child's name.
- Instruct the parent/caregiver on how to use the TP pump to show the proper amount of TP, and how to brush the child's teeth. Have the parent brush off the child's plaque disclosing solution.
- Apply FV to the child's teeth (by dental provider).
- Have the parent/caregiver watch the standardized Anticipatory Guidance presentation on a tablet.

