7.1.2 Baseline (Post-Run-In/Randomization) Visit (Visit 2, $T = 0$ [+10/-2])

- Administer CAPI questionnaire to parent/caregiver.
- Click the REDCap “randomize” button to reveal participant’s randomized assignment to arm. Explain the intervention procedures and rewards program (if assigned to the Intervention Arm) to the parent/caregiver and have her/him explain it back in her/his own words. Explain control procedures (if assigned to the Control Arm) to the parent/caregiver and have her/him explain it back in her/his own words.
- Schedule the family’s next visit (in approximately 3 months) and give the parent/caregiver \$30 compensation for attending the baseline visit.

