7.2 Intermediate Visits

7.2.1 Month 3 Follow-Up Study Visit (Visit 2, $T = \text{business day } 65 \pm 28$)

During this Month 3 follow-up visit, the following procedures will be completed by trained staff members.

- Administer CAPI questionnaire to parent/caregiver.
- Dispense new brush head.
- Dispense earned rewards to the parent/caregiver (*Intervention Arm*).
- Dispense syncing payments to the parent/caregiver (*both groups*).
- Schedule the family’s next visit (in approximately 3 months) and give the parent/caregiver \$30 compensation for attending the 3-month visit.

7.2.2 Month 6 Follow-Up Study Visit (Visit 3, $T = \text{business day } 130 \pm 28$)

During the Month 6 follow-up visit, the following procedures will be completed by trained staff members.

- Perform follow-up assessments of outcome measures and safety.
- Administer CAPI questionnaire to parent/caregiver.
- Record medical history and perform ASTDD BSS dental screening on child participant’s teeth (by blinded dental provider); record decay and assess treatment urgency. Children with urgent treatment needs will be referred with a warm handoff to staff at the corresponding dental clinic.

- Apply plaque disclosing agent to child's teeth (by blinded dental provider).
- Take extraoral photograph(s) of the facial surfaces of child's anterior teeth.
- Brush off plaque disclosing solution.
- Apply FV to the child's teeth (by dental provider).
- Have the parent/caregiver watch the Anticipatory Guidance presentation on a tablet.
- Record weight of TP pump.
- Dispense new toothbrush head and TP pump.
- Dispense earned rewards to the parent/caregiver (*Intervention Arm*).
- Dispense syncing payments to the parent/caregiver (*both groups*).
- Schedule the family's next visit (in approximately 3 months) and give the parent/caregiver \$30 compensation for attending the 6-month visit.
- After this visit, perform FGDs and stakeholder interviews

7.2.3 Month 9 Follow-Up Study Visit (Visit 4, T = business day 195 ± 28)

During the Month 9 follow-up visit, the following procedures will be completed by trained staff members.

- Administer CAPI questionnaire to parent/caregiver.
- Dispense new toothbrush head.
- Dispense earned rewards to the parent/caregiver (*Intervention Arm*.)
- Dispense syncing payments to the parent/caregiver (*both groups*).
- Schedule the family's next visit (in approximately 3 months) and give the parent/caregiver \$30 compensation for attending the 9-month visit.

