7.2.4 Month 12 Follow-Up Study Visit (Visit 5, T = business day 260 ± 28)

The Month 12 visit is the final study visit for participants randomized to the incentive group. During this visit, a trained staff member will complete the final questionnaire and post-test with the parent/caregiver.

- Administer CAPI questionnaire to parent/caregiver.
- Collect the TP pump. Record weight of TP pump.
- Record medical history and perform ASTDD BSS dental screening on child participant's teeth (by blinded dental provider); record decay and assess treatment urgency. Children with urgent treatment needs will be referred with a warm handoff to staff at the corresponding dental clinic.
- Apply plaque disclosing agent to child's teeth (by blinded dental provider).
- Take extraoral photograph(s) of the facial surfaces of child's anterior teeth.
- Brush off plaque disclosing solution.
- Apply FV to the child's teeth (by dental provider) (Continuing delayed control arm only).
- Give the parent/caregiver an electronic tablet to watch the Anticipatory Guidance presentation.
- Give the parent/caregiver the accumulated rewards (*Intervention Group*).
- Distribute 1 new toothbrush head and new TP pump.
- Dispense syncing payments to the parent/caregiver (*both groups*).
- Give the parent/caregiver \$30 compensation for attending this 12-month visit.
- After this visit, perform FGDs.
- *Optional for Control Group only:* Randomize Control Group participants who want to continue into 1 of 2 groups: weekly or quarterly drawing result communication. Explain the intervention procedures and Monetary Rewards program to the parent/caregiver and have her/him explain it back in her/his own words (teachback). Schedule the family's next visit (in approximately 3 months).

7.2.5 Month 15 Follow-Up Study Visit (*Optional for Control Group Only, Visit 6, T = business day 325 ± 28*)

During this Month 15 follow-up visit, the following procedures will be completed by trained staff members.

- Administer CAPI questionnaire to parent/caregiver.

- Dispense new toothbrush head.
- Dispense earned rewards to the parent/caregiver.
- Dispense syncing payments to the parent/caregiver.
- Schedule the family's next visit (in approximately 3 months) and give the parent/caregiver \$30 compensation for attending the 15-month visit.

7.2.6 *Month 18 Follow-up Study Visit (Optional for Control Group Only, Visit 7, T = business day 390 ± 28)*

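### Toothpaste use is analysed as unscaled grams although the visit windows let days of pump use vary from 112 to 168 (pump 1) and from 74 to 186 (pump 2)

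*Combined protocol and SAP*

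**What the plan says.** Section 3.2.2 lists among the secondary oral health measures "TP pump weight change (grams) at Month 6 and Month 12 visits". Section 12.4 names this outcome ("and TP pump weight change") among the numeric outcomes to be fitted with an identity link in a generalized linear mixed model. It specifies no offset, duration covariate or per-day scaling.

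The primary outcome is already a rate: Section 3.2.1 has it "expressed as a mean of the number of qualifying half-day toothbrushing episodes per week".

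The life of each pump follows from the schedule:

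- **Pump 1, start.** Section 7.1.1, "Screening Visit (Visit 1, T = business day -10"), includes the step "Give the family the Oral Hygiene Kit, which includes the smart powered toothbrush and fluoride TP pump".
- **Pump 1, end, and pump 2, start.** Section 7.2.2 places Month 6 at business day 130 ± 28. The pump is weighed and a new one is dispensed. Section 4 confirms the replacement in both groups.
- **Pump 2, end.** Section 7.2.4, "Month 12 Follow-Up Study Visit (Visit 5, T = business day 260 ± 28"), has the pump collected and weighed.

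The visit lists in Section 7 do not mention weighing a pump when it is handed out.

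**The concern.** Grams used between two visits equal daily use multiplied by days of use. If the days differ between families for scheduling reasons, part of the spread in grams has nothing to do with brushing. A family seen late appears to use more toothpaste than an identical family seen early. Pump 2 is affected more because both ends of its interval can move.

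Two things are at stake. The first is precision: scheduling noise makes a real effect on toothpaste use harder to see. The second is comparability: if one arm tends to attend earlier or later, the arms would differ in grams even with the same daily use. The Protocol Summary and Section 4 both name fluoride toothpaste use among the effects to be determined, and pump weight is a measurement separate from the brush count that earns rewards, so it is worth measuring cleanly.

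**Working it through.** The plan gives no power, variance or duration figure for this outcome, so there is none to reproduce. Its primary calculation in Section 12.2 (91 per group, difference 2.65, SD 6.0) does reproduce: 84.2% by the noncentral t, against the stated 84%. It is not an input here.

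**Days of use at the window limits (business days)**

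| Pump | Shortest | Longest | Ratio |
|---|---|---|---|
| 1: day -10 to 130 ± 28 | 102 + 10 = 112 | 158 + 10 = 168 | 1.50 |
| 2: 130 ± 28 to 260 ± 28 | 232 - 158 = 74 | 288 - 102 = 186 | 2.51 |

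Section 7.1.2, "Baseline (Post-Run-In/Randomization) Visit", allows +10/-2 around day 0. If the run-in is therefore read as lasting 8 to 20 business days, pump 1 spans 102 + 8 = 110 to 158 + 20 = 178, a ratio of 1.62.

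**Typical spread, assuming visits uniform and independent within their windows**

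- Pump 1: mean 140, SD 28/√3 = 16.2, coefficient of variation (CV) 0.115. Central 95% of families: 113.4 to 166.6 days, ratio 1.47.
- Pump 2: mean 130, SD √2 × 28/√3 = 22.9, CV 0.176. Central 95%: 86.5 to 173.5 days, ratio 2.0.

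**Variance inflation**

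With grams = daily rate × days, and the two independent, the squared CV of grams is (1 + r²)(1 + c²) - 1, where r is the CV of daily use between families and c the CV of days. Relative to r², the inflation is c²(1 + 1/r²). Here c² = 0.01333 for pump 1 and 0.03093 for pump 2.

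The documents give no r for toothpaste. Two assumed ranges:

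| r | Source | Month 6 | Month 12 |
|---|---|---|---|
| 0.87 | pilot brushing count, Section 12.2, as proxy | 3.1% | 7.2% |
| 0.514 | pilot brushing percentage, Section 12.2, as proxy | 6.4% | 14.8% |
| 0.5 | assumption | 6.7% | 15.5% |
| 0.3 | assumption | 16.1% | 37.5% |

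A comparison with 80% power on the per-day scale would have Φ(2.80/√(1 + inflation) - 1.96) in grams. With the two pilot CVs this is about 78% to 79% at Month 6 and 74% to 77% at Month 12.

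If visits instead follow a triangular distribution over the same windows, the variance of days halves. Inflation with the pilot CVs then falls to about 2% to 3% at Month 6 and 4% to 7% at Month 12.

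**Effect of a timing difference between arms (illustrative)**

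A mean difference of 5 business days in the Month 6 visit changes pump 1 grams by 5/140 = 3.6%. With Month 12 timing unchanged, it changes pump 2 grams by 5/130 = 3.8% in the opposite direction.

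**Even when every visit is on target**, pump 1 covers 140 days, including the pre-randomization run-in, and pump 2 covers 130. Constant daily use would appear as a fall of 10/140 = 7.1% over time in both arms.

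**The case against.** **The ratios are extremes.** This stands. A ratio of 2.5 compares one family at the latest Month 6 and earliest Month 12 visit with another at the reverse. A reader might infer that families commonly differ by that much. Even under uniform timing the central 95% ratio is about 2.0, and less if visits cluster near target.

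**The larger inflation figures rest on an unsourced CV of 0.3 to 0.5.** This also stands. The only related CVs in the documents are for brushing, and they give the smaller figures. Section 8.7.3 has the amount of toothpaste depend on the child's age, which argues against a low CV. Both ranges are therefore shown, and neither is established.

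**Arm bias is conjecture.** A reader might infer that rewards waiting at Months 3 and 6 make the reward arm attend at different times. Section 6.2 does pay drawing rewards at those visits to that arm only. But both arms must attend to collect their syncing payments, and both receive $30 per visit. No passage says that timing differs by arm. If the reward arm did come earlier at Month 6, its pump 1 grams would fall and its pump 2 grams would rise, so the bias would work against the intervention at Month 6 and for it at Month 12.

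**A starting weight may exist.** A reader might infer from the Section 7 lists that change cannot be computed. That goes too far: the pump is one named commercial product (Section 8.7.3), and a separate Manual of Procedures, not available here, may supply the reference weight. What stands is only that the protocol does not state it.

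**Other noise remains.** Section 8.3 asks whether others in the household used the pump, and scaling by days does not remove that. Nor is pump weight the only outcome not self-reported: plaque is scored from photographs by a calibrated central rater (Section 8.1).

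None of this supplies the missing denominator.

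**Conclusion.** The point holds as a minor improvement to a secondary outcome. As written, the plan analyses raw grams over intervals that can differ 1.5-fold and 2.5-fold at the extremes of the permitted windows, and nothing in it corrects for this.

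The likely cost is modest: about 3% to 6% extra variance at Month 6 and 7% to 15% at Month 12 with the pilot brushing CVs as proxy, or about 7% to 16% and 15% to 37% if the CV is 0.3 to 0.5. All of these assume visits uniform and independent within their windows, and daily use unrelated to visit timing.

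Bias between arms is possible but not shown, and its direction could differ between Month 6 and Month 12. It would be wrong to conclude that the toothpaste comparison is biased in favour of the rewards, or that the main result is weakened. The primary outcome is counted per week, and its sample size does not depend on this measure.

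**What to change.** Define the outcome as grams per day: starting weight minus weight at return, divided by the days between the dates on which that pump was handed over and weighed. Adjusting for actual days of use in the model is an acceptable alternative. State which of the two is used in Section 12.4, for Month 6 and Month 12 alike. Use the actual dates of handover and weighing, since under Section 8.8 some visits are remote and the visit date may not be the date the pump changed hands.

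State the reference starting weight, whether measured for each pump or a fixed value for the product.

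The cost is a sentence or two of definition. Pump weights are already entered in REDCap (Section 16.2), which also manages the visit schedule (Section 14). Sections 8.8 and 16.6.1 describe a trial already under way, so weighing pumps at screening may no longer be possible for many families. Dividing by days remains possible for them, with the assumed starting weight stated.
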